## 10. TREATMENT OF SUBJECTS

### 10.1. Description of Study Drug

**Table 3: Investigational Product**

|                                | Investigational Product   |
|--------------------------------|--|
| Product Name:           | Molgramostim nebulizer solution  |
| Dosage Form:            | Nebulizer solution   |
| Unit Dose               | 300 µg   |
| Route of Administration | Inhalation using the PARI eFlow nebulizer (PARI Pharma GmbH)   |
| Physical Description    | Clear, colourless solution containing molgramostim, a recombinant human Granulocyte Macrophage Colony Stimulating Factor (rhGM-CSF).

Excipients are mannitol, polyethylene glycol 4000, Recombumin® Prime, disodium phosphate (anhydrous), citric acid (monohydrate), and water for injection |

### 10.2. Prohibited Medications

The following **prior medications are not allowed** (See exclusion criteria Section 9.2):

- Treatment with inhaled or systemic GM-CSF
- Therapy associated with significant immunosuppression such as systemic prednisolone at a dose equivalent of 10 mg/day or more within 3 months prior to Screening

### 10.3. Treatment Compliance

Subject compliance in the treatment period will be evaluated by unused and used vial counts. Subjects will be asked to return all unused and empty vials at the next clinic visit. Vials will be visually inspected for opening. The number of unused and empty vials will be counted upon return and recorded in the drug accountability log kept at the site.

### 10.4. Randomization and Blinding

Not applicable.

### 10.5. Subject Identification List

The investigator will maintain a list of all subjects screened in the trial at the site. This list includes each subject's identity, date of enrolment and corresponding subject number so that any subject may be identified if required for any reason.

## **11. STUDY DRUG MATERIALS AND MANAGEMENT**

### **11.1. Study Drug**

Each vial of molgramostim contains 300 µg molgramostim in 1.2 mL solution (250 µg/mL).

### **11.2. Study Drug Packaging and Labeling**

All manufacturing and packaging will be performed in accordance with current Good Manufacturing Practice (GMP).

Individual medication kits containing trial medication for four weeks will be supplied in adequate amounts at the dispensing visits.

Labels will comply with local regulations and will be printed in local language.

### **11.3. Study Drug Storage**

The IMP must be stored at 2-8°C.

The IMP will be stored at the trial site or the at the site pharmacy as required by local regulations and laws for the participating sites. The Investigator will ensure that the IMP will be stored in appropriate conditions in a secure location with controlled access. The storage compartment must be monitored and the temperature documented. Any deviations in storage temperature must be reported to sponsor without delay. In case of a temperature deviation, the IMP must not be used until acceptance from the sponsor.

The IMP kits will be dispensed to the subject at Baseline (Visit 2), and at Weeks 4, 8, 12, 16, 20, 24, 32 and 40 (Visits 3, 4, 5, 6, 7, 8, 10 and 12) during the treatment period.

Subjects will be instructed to store the kit at 2-8°C in a safe and secure place out of the reach of children. The IMP should not be frozen or shaken and not be used beyond the expiration date on the vial.

Subjects will be asked to return used and unused medication at the next clinic visit to check compliance.

### **11.4. Study Drug Preparation**

Not applicable.

### **11.5. Administration**

The PARI eFlow nebulizer system (PARI Pharma GmbH, Germany) will be used to administer the IMP. The eFlow Nebulizer Handset is a single subject use, reusable electronic nebulizer. It includes a fine particle aerosol generator (perforated vibrating membrane) defined by a 30L mesh and an aerosol chamber that can produce aerosols with high density of active drug, precisely defined droplet size and a high proportion of respirable droplets.

All subjects, investigators and trial nurses will be trained in IMP administration and medical device maintenance procedure. The training of the subjects will be arranged prior to

administration of the subject's first dose of IMP and checked in clinic on first dosing. The subject will also receive written instructions.

The subject will administer the first dose of IMP at the Baseline visit (Visit 2) under the supervision of trial personnel.

During the treatment period at Weeks 4, 12, 24, 32 and 40 (Visits 3, 5, 8, 10 and 12), subjects will be asked not to take their study treatment prior to the clinic visit because blood samples for laboratory testing will be taken. At these visits dosing will take place in the clinic after the blood samples have been taken. The subject should be instructed to take the last dose the day before the 48-week visit (Visit 14).

### **11.6. Study Drug Accountability**

It is the responsibility of the investigator or trained designee to determine investigational drug accountability and complete the drug accountability log. Drug accountability will be reviewed by the monitor during monitoring visits and at the completion of the trial.

Copies of all Drug Receipt Confirmations, Returned Clinical Supplies Reconciliation Forms and Drug Accountability Logs will be retained in the trial file. These forms are subject to regulatory inspection at any time.

### **11.7. Study Drug Handling and Disposal**

Unused IMP must be returned to supply vendor, or sent for destruction after agreement with the Sponsor, but only after the trial and overall drug accountability has been completed. A list of trial drug, used, or returned must be prepared and signed by the investigator or designee; an account must be given for any discrepancies.

## 12. ASSESSMENTS

The timing of all trial assessments is shown in the Schedule of Procedures in [Table 1](#).

### 12.1. Informed consent

All subjects must provide informed consent in accordance with the origins of the Declaration of Helsinki and the applicable laws of the country. The written informed consent must be obtained before any trial activities are performed, incl. any period for wash-out of concomitant medication.

It is the responsibility of the principal investigator or a sub-investigator to obtain the written informed consent from the subject.

The investigator must explain the nature of the trial, its purpose, the assessments involved, the expected duration, the potential risks and benefits involved and any discomfort it may entail and provide the subject with a copy of the information sheet and the consent form. Information to a subject can be delegated to a nurse, but the investigator must be available for questions and both the nurse and the investigator must sign the consent form to document this.

The subject must be given sufficient time to consider the trial before deciding whether to participate. Each subject must be informed that participation in the trial is voluntary and that he/she may withdraw from the trial at any time and that withdrawal of consent will not affect his/her subsequent medical treatment or relationship with the treating physician.

The subject must sign and date the informed consent form before he/she enters the trial (i.e. before any trial related activity). The investigator must give a copy of the signed informed consent to the subject. The investigator should keep the original.

If information becomes available that may be relevant to the subject's willingness to continued participation in the trial the subject information sheet will be updated by Savara and approved by an IEC/IRB and the Competent authorities. The subject must be informed in a timely manner about the updated subject information sheet and written informed consent must be obtained.

### 12.2. Collection of Sputum Samples for Microbiological Characterization and Quantification

Sputum samples for staining and microscopy, and microbiological culture will be collected at the timepoints shown in in [Table 1](#).

The analysis of the samples will be performed at a specialized mycobacterial laboratory.

If required, induced sputum may be obtained using local standards.

On the days of clinic visits (Visits 1, 2, 3, 4, 5, 6, 7, 8, 10, 12, 14 and 15), subjects will be asked to collect two additional sputum samples at home, preferably on the consecutive days after the site visit. On the days of the telephone contact visits (Visits 9, 11 and 13), three sputum samples will be collected at home, preferably on consecutive days.

The sputum samples must be refrigerated immediately after sampling. Details regarding the collection and handling of sputum samples will be provided in a separate document.

AFB staining (fluorescence and /or ZN stain) will be used to identify NTM in sputum and conduct a semi-quantitative assessment of bacterial load (graded as 0, occasional, 1+, 2+, 3+). Smears will also be fixated on slides and all slides will be submitted to a central laboratory for a second assessment.

Microbiological culture to identify growth of NTM will be conducted using established standards. A semi-quantitative assessment of sputum cultures will be performed. Identification to NTM species level will be conducted on positive samples using established methods.

If sufficient sputum volume is obtained, an additional aliquot will be frozen and stored for potential post-hoc analysis by quantitative polymerase chain reaction (PCR). Such PCR analysis will be performed no later than two years after trial completion. PCR data will not be included in the CTR, but reported separately.

Routine bacteriology and fungal culture will be performed.

### **12.3. Prior and Concomitant Medication**

The subject's use of all concomitant medication must be recorded in the eCRF.

All relevant prior medication should also be recorded. This includes the most recent course of antimycobacterial treatment taken within 3 years prior to the screening visit. Other prior medication should also be recorded if considered relevant by the investigator. Standard information about the medication will be collected including the name of medication, dose, frequency, administration route and treatment period.

Changes to medication not provided as a part of this trial should be kept to a minimum during the trial. However, if considered necessary for the subject's well-being concomitant medication may be given at the discretion of the investigator according to local standard care. All changes will be recorded, including reasons for each change.

In case of worsening of NTM pulmonary disease, antimycobacterial treatment may be added or a dosage increase of antimycobacterial treatment may be applied as rescue treatment, according to investigator's discretion.

At each visit the investigator should ask the subject about use of concomitant medication. All concomitant medication must be documented in the subject's medication records and in the eCRF. Furthermore, each change in concomitant medication (e.g. new treatment, discontinuation of treatment and change in dosage/routine) during the trial must be documented in the same way.

### **12.4. 6-Minute Walk Test (6MWT)**

Exercise capacity will be assessed using the 6MWT at the timepoints shown in [Table 1](#).

The 6MWT will be performed in accordance with European Respiratory Society/American Thoracic Society (ERS/ATS) guidance [[Holland 2014](#)] by technicians with documented training and experience of performing the 6MWT in accordance with the referred ERS/ATS guidance. The 6MWT should be performed twice at each visit in accordance with the ERS/ATS guidelines.

Data from both tests should be entered in the eCRF. Parameters to be recorded comprise pre and post walk dyspnea score using the Borg (CR-10) Dyspnea Score, blood oxygen saturation (SpO2)

(%) at start, worst SpO2 (%) during the walk, distance walked (6MWD; m), duration of the walk (minutes and seconds), O2 flow rate if applicable, reason for stopping early (if applicable).

Trial specific instructions will be provided in a separate document.

If a subject is on long-term oxygen therapy, oxygen should be given at their standard flow rate and held constant throughout the test. The tests conducted after Baseline should be performed using the same oxygen conditions that were used at Baseline.

## **12.5. Patient Reported Outcomes**

The following patient reported outcomes will be assessed at the timepoints shown in [Table 1](#).

A sample of all questionnaires are presented in [Appendix 4](#).

- Clinical symptoms will be assessed using Lower Respiratory Tract Infections – Visual Analogue Score (LRTI-VAS),
- Quality of Life Questionnaire– Bronchiectasis (QOL-B),
- Global Rating of Health (GRH).

### **12.5.1. Lower Respiratory Tract Infections – Visual Analogue Score**

For each of the clinical symptoms of lower respiratory tract infections (dyspnea, fatigue, cough, pain, and sputum) the subject will assess the severity using a 10cm visual analogue scale ranging from 0=no symptoms to 10 =worst possible symptoms. The results from visual analogue scores will be entered in the eCRF.

### **12.5.2. Quality of Life Questionnaire– Bronchiectasis (QOL-B)**

The QOL-B questionnaire in the local language will be used to assess subject’s quality of life. The results from QOL-B will be entered in the eCRF.

### **12.5.3. Global Rating of Health (GRH)**

Global Rating of Health will be assessed as an interviewer questionnaire. Global Rating of Health assesses global health as “excellent, good, fair or poor”. The results from GRH will be entered in the eCRF

## **12.6. Subject Diary**

The subject will receive a subject diary at the timepoints shown in [Table 1](#). The subject diary will include information about the IMP, the use of the nebulizer and home collection of sputum samples. The subject will be asked to record AEs experienced between the visits in the subject diary. The subject will also be asked to place the tear-off label from the IMP box in the subject diary.

## **12.7. Adverse Events**

Any AEs will be reported at every visit from Baseline (Visit 2) to the completion of the 12-week follow-up (Visit 15). Subjects will be encouraged to contact the clinic in between visits if they

experience AEs or have any concerns. For further information of definitions and reporting of AEs and SAEs, see Section 12.15.

## 12.8. Demographic/Medical History/Body Measurements

The following demographic and body measurement data and medical history will be collected at the timepoints shown in Table 1.

- Date of birth
- Weight (kg) in indoor clothes
- Height (cm) without shoes
- Sex
- Race (White/Asian/Black/American Indian or Alaska Native/Native Hawaiian or Other Pacific Islander)
- Smoking (Previous/Current/Never)
- Relevant prior and concurrent disorders
- Prior and current NTM infections including dates and species

## 12.9. Physical Examination

All subjects will undergo a standard physical examination at the timepoints shown in Table 1.

Complete physical examinations will include at a minimum a review of the subject's general appearance, head, eyes, ears, nose, and throat (HEENT), neck, heart, lungs, abdomen, extremities, skin, and general neurological system. Any abnormalities will be recorded in the eCRF and assessed as 'clinically significant' or 'not clinically significant'.

Symptom-oriented or brief physical examinations may be performed as clinically indicated. New abnormal clinically significant physical examination findings not present during the baseline visits should be recorded as AEs and followed during subsequent visits.

## 12.10. Vital Signs

The following vital signs will be assessed at the timepoints shown in Table 1.

- Resting systolic and diastolic blood pressure (mmHg), after 5 minutes sitting
- Resting heart rate (beats per minute), after 5 minutes sitting
- Resting respiration rate (breaths per minute), after 5 minutes sitting
- Oral body temperature (°C)

The observed values will be recorded and assessed as 'normal' or 'abnormal'. Abnormal findings will be assessed as 'clinically significant' or 'not clinically significant'.

## 12.11. Electrocardiogram (ECG)

A 12-lead ECG will be assessed using a standard ECG machine according to local procedures at the time points shown in [Table 1](#).

No central overreading will be performed.

Heart rate, QRS, PR and QT intervals will be recorded from the ECGs. The ECGs will be interpreted and signed and dated by the investigator or his/her designee. Results will be classified as normal, having a non-clinically significant abnormality, or having a clinically significant abnormality. All clinically significant abnormalities will be recorded as AEs.

## 12.12. Radiology

### 12.12.1. CT Scan

If not performed within 6 months prior to Baseline, a CT scan will be performed at the Baseline visit (Visit 2). If there is a decrease in DLCO of at least 20% at two consecutive visits the CT scan may be repeated and the results recorded.

### 12.12.2. Chest X ray (only if conducted as part of the local routine clinical practice)

Chest X-rays are not required for the study but if subjects have a chest X-ray as part of the local routine clinical practice during the study period, the reason and the results from the chest X-ray will be recorded as normal, having a non-clinically significant abnormality, or having a clinically significant abnormality. Clinically significant abnormalities that were not present before the study or that worsened during the study (based on medical records) will be recorded as AEs.

## 12.13. Pulmonary Function Tests

### 12.13.1. DLCO

DLCO will be done using local appropriately calibrated equipment by site staff with documented training in lung function testing at the time points shown in [Table 1](#).

The DLCO measurements should be performed in accordance ATS/ERS guidelines [[Graham 2017](#)]. Parameters to be recorded are DLCO (absolute measured) and DLCO (predicted). The average of two valid tests will be calculated.

### 12.13.2. Spirometry

FEV1 and FVC will be assessed using a local appropriately calibrated spirometer by site staff with documented training in lung function tests at the time points shown in [Table 1](#).

The FEV1 and FVC are measured as 3 valid measurements and the highest value will be entered in the eCRF.

## 12.14. Laboratory Assessments

Blood samples for laboratory assessment will be taken at the timepoints shown in [Table 1](#).

The total amount of blood required for sampling is approximately 240 mL with a maximum of 30 mL for one visit.

All blood samples should be taken **prior to dosing** at the clinic visit.

#### **12.14.1. Levels of Anti-GM-CSF Antibodies**

Analyses for anti-GM-CSF antibodies will be performed at a central laboratory.

#### **12.14.2. Laboratory Safety Assessments**

The laboratory safety analyses (hematology, clinical chemistry and urinalysis) will be performed by a central laboratory at the timepoints shown in [Table 1](#).

Sampling methods and procedures will be in accordance with local routine care. A trial specific laboratory manual for sampling, handling, storage and shipment of samples will be provided to the site personnel. The manual will be provided to the site before start of the trial.

The observed values will be recorded and assessed as ‘normal’ or ‘abnormal’. Abnormal findings will be assessed as ‘clinically significant’ or ‘not clinically significant’.

##### **12.14.2.1. Blood Hematology**

The following parameters will be analyzed:

Hemoglobin, Red Blood Cell Count (RBC), Red Blood Cell Distribution Width (RDW), Hematocrit (PCV/EVF), Mean cell volume (MCV), Mean cell hemoglobin (MCH), Mean cell hemoglobin concentration (MCHC), Platelet count, White cell count, and white cell differential absolute count: Neutrophils, Lymphocytes, Monocytes, Eosinophils, Basophils, and Prothrombin Time International Normalized Ratio (PT-INR)

##### **12.14.2.2. Blood Chemistry**

The following parameters will be analyzed:

Aspartate Aminotransferase (AST), Alanine Aminotransferase (ALT), Gamma Glutamyl Transpeptidase (GGT), Alkaline Phosphatase, Bilirubin, Urea, S-Creatinine, estimated glomerular filtration rate (eGFR), Potassium, Sodium, Calcium, Chloride, Phosphate, Total protein, Albumin, Lactate dehydrogenase (LDH), C-Reactive Protein (CRP), and Glucose (non-fasting)

##### **12.14.2.3. Urinalysis**

The following parameters will be analyzed:

pH, Glucose, RBCs, WBCs, Protein, and Microalbuminuria.

##### **12.14.2.4. Pregnancy Screen**

A serum pregnancy test and contraceptive check will be performed for female subjects at the timepoint shown in [Table 1](#). A urine pregnancy test will also be performed before dosing at Baseline (Visit 2) in order to immediately confirm that the subject is not pregnant.

## **12.15. Adverse and Serious Adverse Events**

### **12.15.1. Definition of Adverse Events**

#### **12.15.1.1. Adverse Event (AE)**

Any untoward medical occurrence in a patient or clinical trial subject administered a medicinal product and which does not necessarily have a causal relationship with this treatment.

An AE can therefore be any unfavorable and unintended sign (including an abnormal laboratory finding), symptom, or disease temporally associated with the use of an IMP, whether or not considered related to the IMP.

#### **12.15.1.2. Serious Adverse Event (SAE)**

Any untoward medicinal occurrence or effect that at any dose:

- Results in death
- Is life-threatening
- Requires hospitalization or prolongation of existing hospitalization
- Results in persistent or significant disability or incapacity
- Is a congenital anomaly or birth defect
- May jeopardize the subject or may require intervention to prevent one or more of the other outcomes listed above (Important Medical Events)

Life-threatening in the definition of a SAE or serious adverse reaction refers to an event in which the subject was at risk of death at the time of event; it does not refer to an event which hypothetically might have caused death if it was more severe.

For important medical events, medical judgement should be exercised in deciding whether an AE/reaction is serious.

The severity of an adverse reaction is largely determined by the outcome of the medical occurrence. An adverse reaction should only be termed "serious" if hospitalization did in fact take place as a result of it. As a rule, hospitalization is the admission to a hospital with at least one overnight stay.

The presentation of a patient in the emergency room (casualty center, health care center) alone without subsequent in-patient admission does not yet fulfill the criterion hospitalization. However, it should be confirmed whether any of the other criteria mentioned above justifies an adverse reaction being classified as "serious" or at least "medically significant."

If the Investigator becomes aware of an SAE with a reasonable relationship to the IMP after the subject has left the trial, this SAE must also be reported (post-trial event).

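### One sentence in Protocol 12.15.1.2, read literally, makes hospital admission a condition for calling any reaction serious and so conflicts with five of the six listed SAE criteria

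*Protocol*

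**What the plan says.** Protocol 12.15.1.2 defines a serious adverse event by six bullet points. One is "Requires hospitalization or prolongation of existing hospitalization". The other five are death, threat to life, disability or incapacity, congenital anomaly or birth defect, and important medical events. None of those five mentions admission.

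The text after the list does several things in turn:

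- It explains that life-threatening means an actual risk of death at the time of the event.
- It adds "For important medical events, medical judgement should be exercised in deciding whether an AE/reaction is serious".
- It ties the severity of a reaction largely to its outcome.
- It then states "An adverse reaction should only be termed 'serious' if hospitalization did in fact take place as a result of it".
- It describes hospitalization as, in general, an admission that includes an overnight stay.
- It says that attending an emergency room or similar facility without admission does not meet the hospitalization criterion, but that sites should check whether another listed criterion makes the reaction serious.

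SAP 10.2.1 repeats the six criteria without the hospitalization-only sentence. It cites Protocol section 12.16 as their source, although they stand in 12.15.1.2.

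**The concern.** The wording makes admission a necessary condition for seriousness, while the list a few lines above makes it one of six sufficient conditions. Both are current protocol text, and they give different answers for the same patient.

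Much depends on the word serious. It is one of the three parts of the SUSAR definition (12.15.1.3). It starts the investigator's 24-hour report (12.17.1) and, through the SUSAR definition, the sponsor's 7-day and 15-day reports (12.17.2). After the last visit, only serious reactions need to be reported at all (12.17.1). The number of SAEs is a safety endpoint (7.3.2), and narratives are written for SAEs (13.3). Section 12.17.3 names no adverse events of special interest, so apart from pregnancy reporting (12.17.5), seriousness is what triggers expedited reporting in this protocol.

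**Working it through.** No arithmetic applies. The check sets the sentence beside each criterion and then follows one example through the reporting rules.

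**Step 1: the sentence against the list**

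| Listed criterion | Does it need admission on its own terms? | Effect of the sentence read literally |
|---|---|---|
| "Results in death" | No | Conflict |
| "Is life-threatening" | No; explained by risk of death at the time | Conflict |
| "Requires hospitalization or prolongation of existing hospitalization" | Yes, or a prolonged stay | Narrowed |
| "Results in persistent or significant disability or incapacity" | No | Conflict |
| "Is a congenital anomaly or birth defect" | No | Conflict |
| Important medical event | No; left to medical judgement | Conflict |

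That gives five direct conflicts and one narrowing. The narrowing has two parts. The list asks whether admission was required, whereas the sentence asks whether it happened. The list also counts a lengthened stay, whereas for a subject already in hospital no admission results from the reaction.

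**Step 2: which events the sentence touches.** It speaks of adverse reactions, and 12.17.1 describes serious adverse reactions as events related to study medication. These are the events that can become SUSARs and the only ones still reportable after the last visit. The restriction therefore falls on the drug-related events.

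**Step 3: one example.** Take a reaction that is related, unexpected and life-threatening, and that is managed without admission.

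| Rule | By the six-item list | By the sentence alone |
|---|---|---|
| Serious (12.15.1.2) | Yes | No |
| 24-hour report (12.17.1) | Due | Not triggered |
| SUSAR (12.15.1.3) | Yes | No |
| Sponsor report (12.17.2) | Within 7 days | Not triggered |
| If it occurs after the last visit (12.17.1) | Reportable | Not reportable |
| SAE count and narrative (7.3.2, 13.3) | Included | Absent |

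**Step 4: would a later check catch it?** The site records seriousness in the eCRF (12.16). The reconciliation in 16.1 compares the SAEs in the safety database with those in the trial database. An event that the site classed as non-serious would be an SAE in neither. Assessment by the CRO (12.17.6) starts from what sites send.

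**Step 5: the severity sentence.** Section 12.15.1.2 says severity is largely determined by outcome. Section 12.16 defines severity as intensity, grades it mainly by interference with daily activity, and records outcome as a separate item. The two descriptions do not match. The context suggests that seriousness was meant in the first.

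**The case against.** The strongest reply is that the sentence should not be read alone. It sits in an explanation of one criterion: the next sentence says what hospitalization is, and the next paragraph calls hospitalization a criterion and directs sites to the others. The explanations of life-threatening and of important medical events carry no admission condition. Section 12.17.2 has its own clock for fatal or life-threatening SUSARs, 12.17.5 requires certain pregnancy outcomes to be reported as SAEs whether or not there was an admission, and SAP 10.2.1 keeps all six criteria. There is also a trial-specific SAE procedure and a Safety Management Plan, neither of which is available here.

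Most of this stands. It shows what the authors intended, and it rules out three stronger readings that a reader might infer:

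- **That the trial defines seriousness by hospitalization alone.** The surrounding text contradicts this.
- **That sites would not report such events.** That assumes a site ignores the list, both explanations and the pointer to the other criteria. The documents support only that a site could fail to report.
- **That the SAP's analysis definition is wrong.** It is intact. Only the classification made at the site, before the data reach the analysis, could be affected.

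The reply does not remove the point. The instruction to check the other criteria is given for patients who attend an emergency room or similar facility and are not admitted. It does not withdraw the sentence, and it does not speak to a reaction managed at home or to a lengthened stay. The SAP describes data already recorded and does not instruct sites.

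On severity, the protocol says largely determined by outcome, which is not the same as equating the two. The mismatch with 12.16 remains but is minor, because the grading rule there is clear.

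**Conclusion.** The point holds as an internal inconsistency in current protocol text. Read literally, one sentence conflicts with five of the six seriousness criteria and narrows the sixth. Read in context, it was probably meant to explain the hospitalization criterion only. Because it is worded as a general rule and never withdrawn, a site following it could fail to report a serious reaction managed without admission: within 24 hours, as a SUSAR, or after the trial.

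The number of affected events is unknown. It depends on how sites read the section and on what the unseen SAE procedure and Safety Management Plan say. A reader might reach for 1/30 = 3.3%, the share that one subject represents among the 30 planned. That is not a rate of missed events and does not measure the problem. The case for correction rests on the wording and on the reporting duties that depend on it.

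**What to change.** Reconcile the passages in Protocol 12.15.1.2:

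1. Limit the sentence to the criterion it seems to explain, for example: *The hospitalization criterion is met only if admission or prolongation of an existing stay did in fact take place.*
2. State that any one of the six criteria is sufficient to make an event or reaction serious.
3. Align the sentence that ties severity to outcome with the intensity definition in 12.16.
4. When the SAP is next revised, correct its cross-reference for the SAE definition to 12.15.1.2.

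The cost is a wording correction and a note to sites, with possibly a few more SAE reports. Any such extra reports would be of events that the six listed criteria already cover. No treatment rule, endpoint or planned analysis changes.
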